Regarding the use of US-PICT, there are multiple studies that support this practice. They recognize it as "an effective and safe treatment in CT, since it produces a significant clinical and radiological improvement"(7). A study carried out in the year 2022, which retrospectively sought to study the results of this technique, culminated demonstrating a significant improvement in pain in patients treated with this technique (11).

Few studies have been conducted to determine which type of therapy is most effective in each case, with very mixed conclusions. In the 2014 systemic review by Louwerens et al, it was shown that both the use of high-energy ESWT and US-PICT are effective treatments in chronic cases of TC for patients with symptomatology longer than 6 months, however it gave greater effectiveness to ESWT.(12) However, [name] et al, in 2014 published a randomized study which concluded that "ultrasound-guided needling treatment was more effective in restoring function and short-term pain relief." (13)

The aim and desire of this study goes a bit further and is outlined below.

3. Main and secondary objectives

1. Main objective:

- The main objective is to compare the mean differences in VAS at 1 month, 3 months and 6 months according to the treatment received, US-PICT or ESWT in patients with TC according to the evolutionary stage of the lesion based on the Bianchi Martinoli classification.

2. Secondary objectives:

- To know if there are variations in functionality with the Latinen test, joint balance (ROM), PGI and CGI.
- To protocolize an attitude towards this type of pathology.
- To favor the use of hospital resources.

4. Design of the study

Design: We propose to conduct a **prospective experimental longitudinal analytical block randomized clinical trial**.

Study population, variables and inclusion-exclusion criteria.

Inclusion criteria:

- Patients aged 30 - 60 years.
- Omoalgia lasting more than 3 months.

- Radiographic and ultrasound visualization in both planes of calcification.
- Sizes > 5 millimeters (mm).

Exclusion criteria:

- Patients not meeting inclusion criteria.
- Presence of another evident cause of pain (joint degeneration, capsulitis, rotator cuff tendon ruptures...).
- Patient who has previously received ESWT or US-PICT.
- Contraindication of therapies: infection, drug allergies, cancer....

Variables to take into account:

- Age: years
- Sex: male/female
- Type of therapy: ESWT/barbectomy

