- Endocrine/rheumatologic diseases: hypothyroidism, diabetes mellitus and rheumatoid arthritis.
- Number of calcifications
- Size of calcifications: mm
- Previous treatments: Yes/ No
- Location of calcification: Supraspinatus, subscapularis, and infraspinatus.
- ROM: Flexion, abduction, and external and internal rotation (°).

- **Visual analgesic scale (VAS):** initial, at 1, 3 and 6 months.

- **Latineen test: initial, at 1, 3 and 6 months of each test variable and final score.**

Correlation of VAS levels and Latineen test: (14)

VAS of 0 - 2.5 → IL = 6 VAS of 2.5-5 → IL=10 VAS of 5-7.5 → IL 13 VAS of 7.5-10 → IL =14

- **Patient Global Impression of Improvement Scale (PGI-I)**
- **Global improvement impression scale (CGI - GI)**

Sample size

Accepting an alpha of 0.05 and a beta of 0.2 in a bilateral contrast, 28 subjects in each arm are required to detect a difference equal to or greater than 3 units on the VAS scale. A standard deviation of 5 is assumed. A loss-to-follow-up rate of 20% has been estimated.

Work plan

The protocol carried out was as follows:

1st Phase : in this first phase, patients will be collected according to the criteria set out above for a period of **12 months**. During this time, the patients will be explained the two possible treatments to be received and after signing the appropriate informed consent, **they will be divided into groups according to treatment (ESWT vs US-PICT) stratifying according to the Bianchi Martinoli classification: (I/II or III)**. The decision for each

treatment will be made randomly, **dividing the patients in a 1:1 ratio** according to whether they come to the initial consultation and the previous patient has received one or the other treatment.

The variables indicated above and in the table of variables will be collected from these patients.

	ESWT	US-PICT
Type I	14n	14n
Type II/III	14n	14n

In relation to **ESWT**, these will be given using a **15 mm transmitter in continuous mode with pressure at 3 bar, frequency 12Hz and 3000 impacts**. The number of sessions will be between 4 - 8 according to the patient's clinical condition with a rest between sessions of 5 to 10 days.

US-PICT will be performed with 1 session in which the following actions will be performed:

- First, a **suprascapular nerve block** will be performed with corticosteroid and anesthetic (3 ml of bupivacaine) in an ultrasound-guided manner.

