- Then **the calcification will be infiltrated** with 5 ml of local lidocaine and preloaded physiological saline solution under ultrasound guidance.
- Finally, **repeated suctioning** with physiological saline will be performed to extract the calcium in an echoguided manner.

The inclusion of patients in the study will be carried out by [name]. The barbotomy technique will be performed jointly by [name], [name] and [name]. The ESWT technique will be performed by Fst. [name].

2nd Phase: Subsequently, 3 revisions will be carried out. One at 1 month, 3 months and another at 6 months after the end of therapy. In these, the variables will be taken again as indicated in the table of variables.

Initial consultation	1 month	3 month	6 month
Age Gender Type of therapy Diseases Number of calcifications Size Previous treatment Location ROM (measurement with goniometer) VAS _{in} Latineen Test	ROM (measurement with goniometer)	ROM (measurement with goniometer)	ROM (measurement with goniometer) VAS _{6m} Latineen Test PGI – I CGI - GI

Table of variables

3rd Phase: The information collected will be synthesized and entered into the SPSS program to obtain the results. For these the following actions will be carried out:

[figure not shown]
- For an independent data design:
 - 2 groups: Student's t-test or Mann-Whitney U-test.
 - More than 2 groups: Analysis of variance or Kruskal-Wallis "H" test.
- For a paired data design:
 - 2 groups: Student's t-test for paired data or Wilcoxon test.
 - More than two groups: Analysis of variance for repeated measures or Friedman's test.

A new variable VAS difference (VASDIF) will be created later, with the data obtained, according to the following formula in order to evaluate the variation with the initial VAS levels.

[figure not shown]
$$\text{VAS}_{\text{in}} - \text{VAS}_{\text{xm}} = \text{VASDIF}_{\text{xm}}$$

Main variables: VAS, Test de Latineen y variables, PGI y CGI.
 Variable agrupadora: ESWT Vs US-PICT

Type I calcifications

Type II/III calcifications

All contrasts will be bilateral and those where $P < 0.05$ will be considered significant. Data will be collected, processed and analyzed with SPSS v.21 statistical software.

Limitations of the study

In order to be able to carry out the following study, the following limitations can be found.

1. Poor adherence to the study by the patients causing losses.
2. Increased waiting times due to ESWT saturation.

Ethical aspects

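### The stated 80% power is for whole arms of 28, but the main objective compares treatments by calcification type at 14 v 14, where power is about 33% on the plan's own inputs

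*Combined protocol and SAP*

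**What the plan says.** The Sample size paragraph in section 4 sets the error rates ("Accepting an alpha of 0.05 and a beta of 0.2 in a bilateral contrast") and concludes that "28 subjects in each arm are required to detect a difference equal to or greater than 3 units on the VAS scale". It adds "A standard deviation of 5 is assumed" and "A loss-to-follow-up rate of 20% has been estimated". It does not mention calcification type, and it does not say whether the 28 already allows for the loss.

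Other parts of the plan point to a comparison within type:

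- Section 3, Main objective: VAS differences between US-PICT and ESWT are compared "according to the evolutionary stage of the lesion based on the Bianchi Martinoli classification".
- Section 4, Work plan, 1st Phase: patients are allocated "dividing the patients in a 1:1 ratio", "stratifying according to the Bianchi Martinoli classification: (I/II or III"). The table below this splits each arm of 28 into 14 Type I and 14 Type II/III.
- Section 4, Work plan, 3rd Phase: ESWT v US-PICT is the grouping variable, followed by separate labels for Type I and "Type II/III calcifications". All contrasts are two-sided at P<0.05.

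Neither a within-type power nor a treatment-by-type test is given anywhere.

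**The concern.** The only power figure in the plan is attached to arms of 28, while the question set as the main objective is answered, on its natural reading, with 14 per arm. A reader would carry the 80% over to each type-specific result.

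The aim is practical. Section 1 wants to know in which cases each therapy should be indicated, and section 3 lists a treatment protocol for the condition as a secondary objective. If power within a type is low, a non-significant result says little, yet it could be taken to support the starting hypothesis that the two treatments give the same VAS differences. A significant result in one type and not the other could become a rule for choosing therapy by type even if the effect were identical in both.

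**Working it through.** **Inputs.** Two-sided alpha 0.05, power 0.80, difference 3, SD 5, 28 per arm and 20% loss come from the Sample size paragraph. The 14 per cell comes from the allocation table, and the independent two-group t-test from the 3rd Phase. The standardised difference is d = 3/5 = 0.6.

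**1. The plan's own figure.** The two-sample formula is n per arm = 2(z₀.₉₇₅ + z₀.₈₀)² × SD²/difference² = 2 × (1.960 + 0.842)² × 25/9 = 43.6, so 44. The t-test version gives 44.6, so 45. Dividing by 0.8 for loss gives 55 to 57. The stated 28 is not reproduced. Two routes do reach it, but neither matches the stated design: the one-sample formula (21.8, so 22; 22/0.8 = 27.5, so 28), or the two-sample formula with SD about 4 and no allowance for loss.

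**2. Power with the planned numbers.** This is the power of the two-sample t-test from the noncentral t distribution, with 2n − 2 degrees of freedom and noncentrality 0.6 × √(n/2). The detectable difference is the one that gives 80% power at SD 5. Loss of 20% leaves 28 × 0.8 = 22.4, taken as 22, and 14 × 0.8 = 11.2, taken as 11.

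| Comparison | n per group | Noncentrality | Power for 3 points | Detectable at 80% |
|---|---|---|---|---|
| Whole arms | 28 | 2.245 | 59.7% | 3.8 |
| Whole arms after loss | 22 | 1.990 | 49.4% | 4.3 |
| Within type | 14 | 1.587 | 33.3% | 5.5 |
| Within type after loss | 11 | 1.407 | 26.8% | 6.3 |

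The normal approximation gives slightly higher power: 61.2%, 51.2%, 35.5% and 29.0%.

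**3. Where the shortfall arises.** From 80% to about 60% is due to the 28 itself. From about 60% to 33% is due to the split by type. Doubling each cell to 28 would therefore bring within-type power only to about 60%; 80% needs 45 evaluable per cell by t-test.

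**4. What two type-specific tests would show.** Suppose a true 3-point difference in both types, with independent tests, each with power p. Both are significant with probability p², exactly one with 2p(1 − p), and neither with (1 − p)².

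| n per cell | Both | Exactly one | Neither |
|---|---|---|---|
| 14 (p = 0.333) | 11% | 44% | 44% |
| 11 (p = 0.268) | 7% | 39% | 54% |

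**5. Dependence on the SD.** The smaller SDs are my assumption; the plan gives only 5.

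| SD | Power at 14 v 14 | Power at 11 v 11 |
|---|---|---|
| 5 (plan) | 33% | 27% |
| 4 | 48% | 39% |
| 3.5 | 59% | 48% |
| 3 | 72% | 61% |
| 2.5 | 86% | 76% |
| 2 | 97% | 92% |

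**The case against.** The strongest objection is that the plan never names a within-type test as primary. The sample size is given per arm, type enters as a stratification factor, and the grouping variable is treatment. The two type labels in the 3rd Phase stand without a sentence around them, and figures there are not shown. This stands in part: the within-type comparison is the natural reading of the objective, table and labels together, but it is an inference. It does not rescue the stated power, because on the other reading the whole-arm comparison has about 60%, not 80%.

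Three stronger readings are tempting, and the documents do not support them:

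- *The split by type takes power from 80% to 33%.* It does not. On the plan's inputs the whole arms never had 80%. For the same reason, it would not be enough to add that the calculation refers to the overall comparison: 80% at 28 v 28 and 33% at 14 v 14 cannot both hold. If 28 per arm did give 80%, 14 would give about 49%.
- *Significance in one type only is the most likely result.* It is common, but at 14 v 14 it is level with neither type reaching significance, and after loss neither is more likely (54% v 39%).
- *Within-type power is below 80% whatever the SD.* It is not. At SD 2.5 it is 86% at 14 v 14, and at SD 2 it is above 90% even after loss. These need an SD no more than half the one the plan assumes.

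It can also be said that making the overall contrast primary would change the research question. That is right, and the correction does not depend on it.

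**Conclusion.** The point holds. The plan attaches 80% power to arms of 28 and gives no power for the comparison by type that its main objective describes. At SD 5, within-type power for 3 points is about 33%, or 27% if the 20% loss comes out of the 14. Only differences of about 5.5 points (6.3 after loss) would be detected with 80% power. A significant result in one type only would be weak evidence that the therapies differ by type, since it would arise in about 44% of trials at 14 v 14 with the same true effect in both.

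This rests on the plan's difference of 3 and SD of 5, equal cells of 14 as in the table, an unadjusted two-sided 0.05 test at one time point, and the within-type reading of the main objective. The plan has three time points and states no multiplicity adjustment; any adjustment would lower power further.

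**What to change.** In the Sample size paragraph, replace the 80% claim with the power that the planned numbers deliver at SD 5: about 60% overall and 33% within type (49% and 27% after 20% loss). Alternatively, give the detectable differences at 80% power: 3.8 and 5.5 points before loss. State whether the 28 and 14 are before or after loss.

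In the 3rd Phase:

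- Report the Type I and Type II/III differences in VASDIF each with a 95% CI.
- Add the overall US-PICT v ESWT difference in VASDIF adjusted for type, and the treatment-by-type interaction estimate with its 95% CI.
- State that no claim that the therapies differ by type will rest on significance in one type only.

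Whether the overall contrast should replace the within-type one as primary is for the sponsor to decide. Whichever is chosen, the text should say which comparison the power figure belongs to.

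The cost is wording and a small addition to the analysis, with no extra patients, visits or measurements. The stated figures become less favourable and the type-specific conclusions more cautious.

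### The sample size rests on an unsourced SD of 5, the ceiling for a single 0–10 VAS score and not tied to the change score analysed; at that SD the stated 3-point detectability does not hold

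*Combined protocol and SAP*

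**What the plan says.** Section 4, Sample size, sets the error rates ("Accepting an alpha of 0.05 and a beta of 0.2 in a bilateral contrast") and states that "28 subjects in each arm are required to detect a difference equal to or greater than 3 units on the VAS scale". It then adds "A standard deviation of 5 is assumed" and "A loss-to-follow-up rate of 20% has been estimated". It gives no source for the SD and does not say whether it belongs to a single VAS score or to a change.

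The list of variables in the same section pairs VAS bands with Latineen values. The lowest band starts at 0 and the highest ends at 10, so the scale is 0–10.

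The Work plan allocates by "dividing the patients in a 1:1 ratio". Its table puts 14 patients in each combination of treatment and calcification type (I, and II/III), which makes 28 per arm.

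Under 3rd Phase, VASDIF is defined as initial VAS minus VAS at month x, "in order to evaluate the variation with the initial VAS levels". Independent groups are compared by Student's t-test or the Mann-Whitney U-test, two-sided at 0.05. The main objective (section 3) is the treatment comparison of VAS differences by ultrasound type. No power or detectable difference is given within type.

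**The concern.** An SD equal to the mathematical maximum for the scale is not a credible planning value for a single score, and the plan gives nothing to support it. The plan also states the SD for the VAS scale while analysing a change score. The SD of a change depends on the baseline SD, the follow-up SD and their correlation, and the plan mentions none of these.

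The SD determines what 28 per arm can show. If it is wrong, or belongs to another variable, the sponsor does not know whether a 3-point difference is within reach overall. There is also no basis for judging the by-type comparison, which is the main objective and has half the patients.

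**Working it through.** **Inputs from the plan.** Two-sided alpha 0.05; power 0.80; difference 3; SD 5; 28 enrolled per arm; 14 enrolled per type and arm; loss 20%. Evaluable: 28 × 0.8 = 22.4, taken as 22 per arm; 14 × 0.8 = 11.2, taken as 11 per cell.

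**1. Can 28 be reproduced?** With z-values 1.960 and 0.842:

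- Two independent arms: n = 2 × [5 × (1.960 + 0.842)/3]² = 43.6, so 44 evaluable per arm; 44/0.8 = 55 enrolled. This is not 28.
- One-sample or paired: n = [5 × (1.960 + 0.842)/3]² = 21.8, so 22; 22/0.8 = 27.5, so 28. This matches, but it lacks the factor 2 that two independent arms require.

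The plan does not say which formula was used. The match shows only that 28 agrees with the one-sample form and not with the two-arm form.

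**2. Ceiling for a single score.** On a 0–10 scale with mean m, the largest SD is √[m(10 − m)]. This is 5.0 at m = 5, 4.9 at m = 4 or 6, and 4.58 at m = 3 or 7. (With the n − 1 divisor and n = 28 the sample value can reach 5.09.)

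**3. Ceiling for VASDIF.** VASDIF runs from −10 to +10, so its largest SD is 10. An SD of 5 is therefore possible. To see how large it is, use SD(change) = √(s₀² + s₁² − 2·r·s₀·s₁) with assumed values, none of them in the documents: baseline SD s₀ of 1.5–2.5, follow-up SD s₁ of 2–3, correlation r of 0–0.5.

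- Low end: √(1.5² + 2² − 2 × 0.5 × 1.5 × 2) = √3.25 = 1.80.
- High end: √(2.5² + 3²) = √15.25 = 3.91.

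Under these assumptions the SD of VASDIF is about 1.8–3.9.

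**4. What the planned numbers can detect.** For the two-sample t-test at 80% power, the detectable difference is about 0.865 × SD with 22 per arm and 1.256 × SD with 11 per cell.

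| SD of VASDIF | Overall, 22 per arm: detectable difference | Overall: power for 3 points | Within type, 11 per cell: detectable difference | Within type: power for 3 points |
|---|---|---|---|---|
| 2 (assumed) | 1.7 | >99% | 2.5 | 92% |
| 2.5 (assumed) | 2.2 | 97% | 3.1 | 76% |
| 3 (assumed) | 2.6 | 90% | 3.8 | 61% |
| 3.5 (assumed) | 3.0 | 79% | 4.4 | 48% |
| 3.9 (assumed) | 3.4 | 70% | 4.9 | 40% |
| 5 (plan) | 4.3 | 49% | 6.3 | 27% |

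The SD at which 22 per arm just reach 80% power for 3 points is 3/0.865 = 3.47, or about 3.5.

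If nobody were lost, 28 per arm at SD 5 would still give only about 60% power for 3 points, with a detectable difference of 3.8.

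**The case against.** The strongest reply is that an SD that is too large, used correctly, only makes a trial larger than it needs to be. This is right as a general rule. The shortfall at SD 5 therefore comes from the step from the inputs to 28, not from the size of the SD. The rule does not rescue the paragraph, because the SD was not carried into a two-arm calculation: 28 is below the 44 evaluable that SD 5 would require.

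A second reply is that the ceiling of 5 applies to the wrong variable, since VASDIF can have an SD of up to 10. This also stands. A reader might infer that SD 5 is impossible for the analysed outcome, and the documents do not support that. The ceiling for VASDIF falls to 5 only among patients with the same starting VAS, and the inclusion criteria set no baseline VAS.

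A reader might also infer that, because 5 looks too high, the trial can detect less than 3 points. The documents do not show this. Over the assumed SD range of 1.8–3.9, the detectable difference with 22 per arm runs from about 1.6 to 3.4, on both sides of 3.

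Finally, a reader might say that the plan misstates its within-type power. It states none, so there is nothing there to misstate.

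**Conclusion.** The SD is wrong as written: it is unsourced, it equals the maximum for the variable it names, and it is not tied to the variable analysed. The sample-size statement built on it also fails on its own inputs. At SD 5 with 20% loss, power for 3 points is about 49% instead of 80%, and the detectable difference is about 4.3 instead of 3. These two figures assume 22 evaluable per arm and a two-sample t-test, and otherwise use only the plan's numbers.

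The 3-point claim may still prove true. It does so with 22 evaluable per arm if the SD of VASDIF is about 3.5 or less, which covers most but not all of the assumed range. Whether 28 per arm is enough therefore stays open until the SD is sourced. Within type, 3 points is detectable at 80% power with 11 per cell only if the SD is about 2.4 or less (3/1.256 = 2.39).

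**What to change.** Rewrite the Sample size paragraph as follows.

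- Replace SD 5 with an SD for VASDIF and give its source. The department's own records, or the randomised comparison of the two treatments cited in section 2, are the obvious places to look.
- Name the outcome and time point to which the SD and the 3-point target refer.
- Use the two-independent-sample formula. State the difference detectable at 80% power for 28 enrolled (22 evaluable) per arm.
- Add the same figure for 14 enrolled (11 evaluable) per type cell. This is an addition, since the plan gives none now.
- Show a sensitivity range that includes the unfavourable end, such as SD 2, 2.5, 3, 3.5, 3.9 and 5. This gives 1.7, 2.2, 2.6, 3.0, 3.4 and 4.3 overall, and 2.5, 3.1, 3.8, 4.4, 4.9 and 6.3 within type.
- Do not claim better detectability than 3 points until the SD is sourced.

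The rewrite costs one paragraph and a search of existing data. If the sourced SD exceeds about 3.5, the sponsor must either accept a larger detectable difference or enrol more patients.

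### The arm depends on the previous patient's treatment and nothing conceals it, so half to nearly all assignments could be known in advance

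*Combined protocol and SAP*

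**What the plan says.** Section 4 (Design of the study) describes a "prospective experimental longitudinal analytical block randomized clinical trial". Under Work plan, 1st Phase, consenting patients are split 1:1 between ESWT and US-PICT, stratified by Bianchi Martinoli type, and the plan says that the choice of "treatment will be made randomly". The same sentence then gives the mechanism: the arm is set "according to whether they come to the initial consultation and the previous patient has received one or the other treatment". The accompanying table plans 14 patients per arm in Type I and 14 per arm in Type II/III.

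No section gives a sequence, a block size, a list holder, envelopes, central allocation or any other concealment. The plan says "The inclusion of patients in the study will be carried out by" a named member of staff, and it says who performs each technique, but not who allocates. The one outside person, under Ethical aspects, is there for data anonymity.

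On timing, the 1st Phase text describes the division into groups and then adds: "The variables indicated above and in the table of variables will be collected from these patients". The Table of variables lists, for the initial consultation, "Age Gender Type of therapy Diseases Number of calcifications Size Previous treatment Location ROM", followed by initial VAS. It gives no order within the visit.

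**The concern.** A rule that depends on the previous patient's treatment works only if whoever applies it knows that treatment. No masking is described, and the arms differ visibly: one US-PICT procedure against 4 to 8 ESWT sessions. An enroller in that position may foresee the next arm and can act on it by deferring a patient, changing the order, or applying an exclusion that involves judgement, such as "Presence of another evident cause of pain".

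The main objective is a between-treatment comparison by lesion type, with 14 patients per cell, so redirecting a few patients can matter. VASDIF subtracts baseline VAS "in order to evaluate the variation with the initial VAS levels", but the listed tests are unadjusted. They would not correct imbalance in calcification size, endocrine disease or symptom duration, and the last of these is not among the listed variables. Bias that enters at recruitment cannot be reliably removed in analysis. The label matters too: if the rule is alternation, the trial is quasi-randomised, not block-randomised.

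**Working it through.** **Inputs.** From the 1st Phase table: 14 per arm in each of two lesion types, so 28 per type and 4 × 14 = 56 in all. This agrees with 2 × 28 from Sample size. The plan gives no figure for predictability, so there is none to reproduce. Assumption throughout: the enroller knows past assignments.

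**Step 1: the readings.** (a) Alternation, either within lesion type or in one overall sequence. (b) Blocks of two, the first member random and the second receiving the other arm. The text does not settle between them, nor whether the previous patient is counted overall or within lesion type.

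**Step 2: assignments known with certainty.**
- Alternation leaves only the first patient of each sequence unknown: 54/56 = 96% within type, 55/56 = 98% overall.
- Blocks of two reveal every second patient: 28/56 = 50%.

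**Step 3: share guessed correctly, g.** A guesser names the arm with fewer patients so far in that lesion type and tosses a coin at ties. Completed blocks are balanced, so this needs no knowledge of block sizes.
- Alternation: (27 + 0.5)/28 = 0.982 within type; (55 + 0.5)/56 = 0.991 overall.
- Permuted block of size 2m: expected correct = m + (4^m/C(2m,m) − 1)/2.
  - m = 1: 1 + (4/2 − 1)/2 = 1.5 of 2 = 0.750
  - m = 2: 2 + (16/6 − 1)/2 = 2.833 of 4 = 0.708
  - m = 3: 3 + (64/20 − 1)/2 = 4.1 of 6 = 0.683
- A list of four blocks of 4 and two of 6 (16 + 12 = 28): (4 × 2.833 + 2 × 4.1)/28 = 0.698.
- A list of one block of 4 and four of 6 (4 + 24 = 28): (2.833 + 4 × 4.1)/28 = 0.687.

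**Step 4: selection-bias index.** Suppose the enroller shifts the prognosis of the next patient by +δ or −δ according to the guess. The expected mean shift is δ(2g − 1) in one arm and −δ(2g − 1) in the other, a difference of 2δ(2g − 1). Expected bias is therefore proportional to 2g − 1.

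| Rule | g | Certain | 2g − 1 |
|---|---|---|---|
| Alternation, overall | 0.991 | 98% | 0.982 |
| Alternation within type | 0.982 | 96% | 0.964 |
| Blocks of two | 0.750 | 50% | 0.500 |
| Four blocks of 4, two of 6 | 0.698 | 11.2% | 0.395 |
| One block of 4, four of 6 | 0.687 | 15.5% | 0.374 |

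The last two entries under Certain come from 4,000 simulated sequences, supposing that the mix of block sizes leaks but not their order.

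**Step 5: gain from the mixed-block list.** Against alternation within type: 1 − 0.395/0.964 = 59% and 1 − 0.374/0.964 = 61%. Against blocks of two: 1 − 0.395/0.500 = 21% and 1 − 0.374/0.500 = 25%.

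**Step 6: why fix the total.** Blocks of 4 and 6 drawn freely and cut at 28 ended unequal in 22.7% of 40,000 simulated strata. The table calls for 14/14.

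**The case against.** The strongest reply is that the sentence is awkward translated English and that the design label, the word for random and the 1:1 ratio all point to blocks of two with a random first member. On that reading the patients are randomised and there is no contradiction with the label; the 98% and the 59–61% reduction then do not apply. This stands as far as it goes: the contradiction is strict only under alternation. But half the arms are still known in advance, and concealment is still undescribed.

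Several smaller points also stand. Consent already precedes allocation in the text, and stratification means that the lesion type must be known first, so what mainly needs stating is that baseline VAS comes before the arm is revealed. The Table of variables shows nothing about order within a visit. The exclusion criterion has listed examples and imaging is already required, which narrows discretion, although the list is open-ended. With names removed, nobody can tell whether the enroller also treats or applies the rule, so foreknowledge is inferred and not stated.

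Finally, the index compares lists under known past assignments. It does not measure the benefit of concealment, which is the larger part of the remedy. That is a reason not to lean on the block arithmetic; it does not weaken the case for a concealed list.

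**Conclusion.** The concern holds and should be resolved before any further patient is allocated. As written, the rule leaves between half of the assignments (blocks of two) and 96–98% of them (alternation) known beforehand to anyone who sees the previous assignment. The wording does not settle which reading applies. These figures rest on the planned 28 patients per lesion type and on the enroller knowing past assignments. The latter is plausible, given visibly different treatments and no described concealment, but it is not stated in the plan. The effect on the treatment comparison cannot be expressed in VAS points from the documents.

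**What to change.** For all patients not yet allocated:

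- Replace the rule with a computer-generated 1:1 list stratified by Type I against Type II/III. Reconcile the bracketed grouping in the 1st Phase text, which can be read as putting Types I and II together, with the table.
- Use permuted blocks of undisclosed size in random order, constrained to 14/14 per type. Four blocks of 4 and two of 6, or one of 4 and four of 6, are examples; recompute the mix if the sample size changes.
- Have the list held by someone who neither enrols nor treats. The external person under Ethical aspects is one candidate, if willing.
- Reveal the arm by sealed opaque envelopes or central allocation, only after consent, eligibility, lesion type and baseline VAS are recorded.

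For patients already allocated, state which rule was applied. Report any who were alternated as quasi-randomised, with a sensitivity analysis excluding them if others were allocated from the new list. If everyone was allocated by the old rule, describe it accurately and add it to Limitations of the study.

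The documents do not settle whether recruitment is open: the Work plan opens in the past tense and continues in the future. If it is open, the cost is a short amendment, a one-off list and an independent holder, with no extra patients or visits. The sensitivity analysis would rest on fewer patients, all recruited later, so it would be imprecise. If recruitment is complete, only the description and the limitations can change.

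### The table of variables, as it reads, lists only ROM at 1 and 3 months, in conflict with the main objective (VAS) and the variable list (VAS and Latineen test)

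*Combined protocol and SAP*

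**What the plan says.** The main objective (section 3) is to "compare the mean differences in VAS at 1 month, 3 months and 6 months according to the treatment received", by evolutionary stage of the lesion. The starting hypothesis in section 1 names the same three times.

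The list of variables in section 4 sets the collection times for two scales: "Visual analgesic scale (VAS): initial, at 1, 3 and 6 months" and "Latineen test: initial, at 1, 3 and 6 months of each test variable and final score".

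Two sentences in the Work plan then say what is to be collected:

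- 1st Phase (recruitment and allocation): "The variables indicated above and in the table of variables will be collected from these patients".
- 2nd Phase (the reviews at 1, 3 and 6 months after therapy ends): "In these, the variables will be taken again as indicated in the table of variables".

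In the table of variables, the initial column ends with the baseline VAS and the Latineen test. The 1-month and 3-month columns each hold one entry, ROM by goniometer. The 6-month column holds ROM followed by "VAS _{6m} Latineen Test PGI – I CGI - GI".

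The 3rd Phase defines VASDIF at x months as the initial VAS minus the VAS at x months.

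**The concern.** The sentence that governs the follow-up visits points to the table and to nothing else. Someone running a 1-month or 3-month review from that table would measure ROM and stop. Yet the main objective rests on a VAS value at each of those visits, and VASDIF cannot be formed without one.

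A pain score that is not taken at the visit is gone. Under Resources required, the data come from the clinical database, and the plan names no other source from which a missed score could be recovered. The correspondence between VAS bands and Latineen scores given in the variable list would not help, because both scales are absent from the same two columns.

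**Working it through.** The plan gives no figure on this point, so the check sets its statements side by side. The sample size of 28 per arm does not enter.

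**Step 1. Follow-up times at which each place requires or shows VAS and Latineen**

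| Place | VAS | Latineen |
|---|---|---|
| Starting hypothesis (section 1) | 1, 3, 6 months | not mentioned |
| Main objective (section 3) | 1, 3, 6 months | not applicable |
| Variable list (section 4) | 1, 3, 6 months | 1, 3, 6 months |
| VASDIF formula (3rd Phase) | each month x analysed | not applicable |
| Table of variables, as it reads | 6 months only | 6 months only |

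The conflict is confined to these two scales. ROM appears at every visit. The two global impression scales appear only at 6 months, and the variable list gives them no times, so nothing contradicts the table there.

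**Step 2. Which instruction governs the follow-up visits**

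The 1st Phase sentence joins the list and the table. Read that way, VAS and Latineen are due at all three reviews. The 2nd Phase sentence is the one written for the reviews, and it names only the table. Read that way, they are due at 6 months only. The plan does not say which prevails.

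**Step 3. What can be computed under each reading**

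- List and table together: VASDIF at 1, 3 and 6 months, so 3 of 3 time points.
- Table alone: VASDIF at 6 months, so 1 of 3 time points; 3 − 1 = 2 are missing. The same count holds for the follow-up Latineen scores.

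The comparison is made within two calcification strata. The plan describes the split in two ways (I/II or III in the text; I against II/III in the allocation table), but there are two strata either way. That gives 3 × 2 = 6 treatment comparisons of VASDIF. The table alone supports 1 × 2 = 2, which leaves 6 − 2 = 4 without data. The total of 6 is a count made here; the plan does not list its comparisons.

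**Step 4. Effect on the analysis menu**

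Under the table alone, VAS would have two time points, initial and 6 months. The 3rd Phase option for more than two paired measurements (repeated-measures analysis of variance or Friedman's test) would then have no VAS series to work on.

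**The case against.** The strongest reply is that the design is clear and only the table is out of step. The hypothesis, the objective, the variable list and the VASDIF formula all require or presuppose VAS at 1 and 3 months, and the 1st Phase sentence says that the listed variables are collected as well as those in the table. This stands. A reader might infer from the table that the plan omits these measurements and that two of the three main comparisons could not be computed. The documents do not support that: the variable list schedules VAS at "initial, at 1, 3 and 6 months", and under it all three time points can be computed.

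The second reply is that the table was read from a PDF by a program and may have lost entries. This also stands. The table's columns are run together in the text, and figures are missing nearby. The label for VAS at 6 months suggests a month-indexed series in which entries for 1 and 3 months would be expected. On the other side, the two outer columns look complete and both middle columns show the same single entry. That pattern fits a real gap, but it also fits a parsing loss affecting both columns alike. The text gives no basis for saying which is more likely.

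Neither reply removes the ambiguity. The 1st Phase sentence belongs to recruitment, and the later instruction written for the reviews still points to the table alone.

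**Conclusion.** The point holds as an internal inconsistency: as it reads, the table of variables does not match the main objective or the variable list on when VAS is collected, nor the variable list on when the Latineen test is collected.

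The loss depends on two assumptions, neither of which the documents establish: that the middle columns lack these entries in the source, and that staff follow the table alone despite the variable list. If both are true, VASDIF is missing at 2 of 3 main-objective time points (4 of 6 comparisons on the count above), as are 2 of 3 follow-up Latineen scores. If either is false, nothing is lost. Confidence is low to medium until the source table is checked. The point still deserves action, because it concerns main-endpoint data that cannot be recovered once the visits have passed.

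**What to change.** Check the source table of variables. If the 1-month and 3-month columns already carry VAS and the Latineen test, the matter is closed.

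If they do not, add VAS at 1 month and the Latineen test to the 1-month column, and VAS at 3 months and the Latineen test to the 3-month column, so that the visit schedule agrees with section 3 and the variable list. It would also help if the 2nd Phase sentence referred to the variable list as well as the table, as the 1st Phase sentence does.

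The cost is a table correction and a few minutes per patient at visits already planned. No treatment, visit or sample size changes.
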